## APPENDIX 4 HOLTER RECORDING AND ANALYSIS

Continuous 12-lead ECGs (Holters) will be recorded using the Mortara Surveyor system.

The continuous 12-lead digital ECG data will be stored and transmitted to iCardiac using the appropriate medium (e.g., file transfer protocol [FTP], disc, or flash drive). ECGs to be used in the analyses will be selected by pre-determined time points as defined in the Schedule of Assessments and Procedures, and will be read centrally by iCardiac Technologies, Inc.

The following principals will be followed in iCardiac's core laboratory:

- ECG analysts are blinded to the subject, visit and treatment allocation
- Baseline and on-treatment ECGs for a particular subject will be over-read on the same lead and will be analyzed by the same reader.
- The primary analysis lead is lead II. If lead II is not analyzable, then primary lead of analysis will be changed to another lead for the entire subject data set.

The following is a brief description of ECG analysis methods utilized by iCardiac' core laboratory.

### TQT Plus ECG Extraction Technique

Ten 14-second digital 12-lead ECG tracings will be extracted from the continuous Holter recordings using the “TQT Plus method”, a computer-assisted and statistical process utilized by iCardiac Technologies. The method enables extraction of ECGs with the lowest HR variability and noise within the protocol-specified extraction time window (e.g., the HR and QT changes from beat-to-beat in the range of <10%). At each protocol-specified timepoint, 10 ECG replicates will be extracted from a 5-minute “ECG window” (typically, the last 5 minutes of the 15-minute period when the subject is maintained in a supine or semi-recumbent quiet position).

### High-Precision QT Analysis

High-precision QT analysis will be performed on all analyzable (non-artifact) beats in the 10 ECG replicates. Statistical quality control procedures are used to review and assess all beats and identify “high” and “low” confidence beats using several criteria, including:

- QT or QTc values exceeding or below certain thresholds (biologically unlikely).
- RR values exceeding or below certain thresholds (biologically unlikely).
- Rapid changes in QT, QTc or RR from beat to beat.

Measurements of all primary ECG parameters (QT, QTc, RR) in all recorded beats of all replicates that are deemed “high confidence” is performed using COMPAS software. All low confidence beats are reviewed manually and adjudicated using pass-fail criteria. The final QC assessment is performed by a cardiologist. The beats found acceptable by manual review are included in the analysis. The median QT, QTc, and RR value from each extracted replicate is

calculated, and then the mean of all available medians from a nominal timepoint is used as the subject's reportable value at that timepoint.

Categorical T-wave morphology analysis and the measurement of PR and QRS intervals will be performed manually in 3 of the 10 ECG replicates at each timepoint. Each fiducial point (onset of P-wave, onset of Q-wave, offset of S-wave, and offset of T-wave) is electronically marked.

#### **T-wave morphology categories (assessed manually)**

Category	Description
Normal T-wave	Any T-wave not meeting any criterion below
Flat T-waves	T amplitude < 1 mm (either positive or negative) including flat isoelectric line
Notched T-wave (+)	Presence of notch(es) of at least 0.05 mV amplitude on ascending or descending arm of the positive T-wave
Biphasic	T-wave that contains a second component with an opposite phase that is at least 0.1 mV deep (both positive and negative/positive and polyphasic T-waves included)
Normal T-wave (-)	T amplitude that is negative, without biphasic T-wave or notches
Notched T-wave (-)	Presence of notch(es) of at least 0.05 mV amplitude on descending or ascending arm of the negative T-wave

In addition to the T-wave categorical analysis, the presence of abnormal U-waves is noted.

## **APPENDIX 5 REPEAT COHORT USING DIFFERENT DOSAGE FORMULATION**

Procedures and analyses as outlined in this protocol will be the same, with the following exceptions:

- The dose of TBI-223 will be delivered in enteric capsules.
- All subjects will receive active treatment.
- A minimum of 6 subjects is needed. Ideally, all 8 subjects who participated in the original cohort will participate in the re-dose cohort. If less than 6 subjects from the original cohort agree to participate, additional subjects will be screened as needed in order to dose a minimum of 6 subjects.
- Repeat subjects will be assigned a new subject number so as not to break the blinding of the original cohort.
- The repeat cohort will not be blinded (blinding is not necessary because all subjects will receive the same treatment).
- Cardiac telemetry and Holter recording will not be performed during the re-dose cohort.
- Subjects will check-in on Day -1 instead of Day -2. With the exception of cardiac telemetry and Holter monitoring, the procedures that were previously scheduled for Day -2 will be performed on Day -1. The Day -1 results will be used to qualify repeat subjects for study participation. If additional subjects are needed, they will undergo screening to qualify for the study.
- Neurological examinations will be performed at Screening, Day -1, and at 3 and 48 hours postdose.

## APPENDIX 6 PART 2 OF THE STUDY

Procedures and analyses as outlined in this protocol will be the same, with the following exceptions:

The dose of TBI-223 will be delivered as follows in Cohort 8:

- Arm 1 – TBI-223 SR Tablets (Prototype 1) - 1800 mg dose (3 x 600 mg tablets), under fed conditions
- Arm 2 – TBI-223 SR Tablets (Prototype 2) - 1800 mg dose (3 x 600 mg tablets), under fed conditions
- Arm 3 – TBI-223 SR Tablets (Prototype 3) - 1800 mg dose (2 x 900 mg tablets), under fed conditions
- Arm 4 – TBI-223 IR Tablets - 2000 mg dose (2 x 1000 mg tablets), under fasting conditions

In Cohort 9, the subjects from Cohort 8, Arm 4, who received the IR tablet formulation will be brought back following a 7-day washout and administered TBI-223 IR tablets, 2000 mg dose (2 x 1000 mg tablets), under fed conditions.

- A minimum of 6 subjects per treatment arm in Part 2.
- Part 2 will not be blinded (blinding is not necessary because all subjects will receive the same treatment).
- Cardiac telemetry and Holter recording will not be performed during Part 2. Subjects will check-in on Day -1 instead of Day -2. With the exception of cardiac telemetry and Holter monitoring, the procedures that were previously scheduled for Day -2 will be performed on Day -1. The Day -1 results will be used to qualify repeat subjects for study participation. If additional subjects are needed, they will undergo screening to qualify for the study.
- Neurological examinations will be performed at Screening, Day -1, and at 3 and 48 hours postdose.

**Table 16 Schedule of Assessments, Part 2**

STUDY DAY	SCR	CONFINEMENT																		FU				
		-28 to -2	-1 CI	DAY 1										DAY 2				3	4					
				STUDY HOUR																				
EVENT				0	0.5	1	1.5	2	3	4	5	6	7	8	12	16 a	20	24	30	36	42	48	72	N/A
Serum pregnancy (females only)	X	X																						
FSH (post-menopausal females only)	X																							
Concomitant medication review	X			<-----X----->																				
Check-in questions		X																						
Adverse events f	X	X	X		X		X	X	X		X		X	X	X	X	X	X	X	X	X	X		
High-fat, high-calorie breakfast g			X																					
Dose			X																					
PK blood collection h			X	X	X	X	X	X	X	X	X	X	X	X	X	X	X	X	X	X	X	X		

CI = check-in; ECG = electrocardiogram; FSH = follicle-stimulating hormone; FU = follow up; HIV = human immunodeficiency virus; N/A = not applicable; PK = pharmacokinetic; SCR = screening; T and R = temperature and respirations

- a. The 16-hour time point following dosing on Day 1 will either be on Day 1 or Day 2, depending upon time of dosing on Day 1.
- b. A detailed neurological exam will be conducted by a licensed physician or suitably medically qualified designee at both scheduled and unscheduled time points as deemed necessary by the Investigator. The neurological examination is planned to be performed around the estimated  $T_{max}$  (currently estimated at 3 hours post dosing; this time could change based on data generated during the study). Timepoints can be altered based on generated PK data.
- c. Vitals signs will be measured at screening, check-in, and while subjects are in confinement. Vitals signs will be measured within 90 minutes prior to dosing and within 15 minutes of the remaining defined time points in flowchart. Both blood pressure and heart rate (pulse) should be captured simultaneously. Blood pressure and heart rate should be measured after subjects are in a seated position for at least 2 minutes and then again after standing for 1 minute, except when they are supine or semi-reclined because of study procedures and/or adverse events, or as deemed necessary by the Investigator.
- d. 12-lead safety ECGs will be printed and reviewed on-site by the Principal Investigator or designee. TriPLICATE ECGs will be completed at screening, Day -2, Day -1, and at 48 hours only. All other time points will be single ECG readings within 15 minutes at time points within flowchart. The predose ECG should be performed prior to the pre-dose blood draw. If a subject experiences a post-dosing QTcF  $>500$  msec or a change-from-baseline QTcF  $>60$  msec, after repeat testing, additional ECGs should be recorded until normalization or return to baseline.
- e. The first ECG may be done within 2 hours prior to dosing and must be completed 20 minutes prior to the pre-dose blood draw. All safety ECGs on Day 1 and Day 2 will be extracted from a continuous 12 lead Holter recording at discrete timepoints as noted in above flow chart and Day -1 will be extracted at the same time as vital sign measurements.
- f. Subjects will be monitored for treatment-emergent adverse events from the time of dosing and throughout the study via safety assessments, observation, and subject reporting. A specific inquiry regarding adverse events will be conducted prior to dosing and at time points determined by the Investigator postdose and upon return to clinic for subsequent visits. The inquiry to collect adverse events using non-leading questions on Day 11 ( $\pm 1$  day) will be done via a phone call.
- g. In Part 2, Cohort 8, Arms 1-3 and Cohort 9, a high-fat, high-calorie breakfast meal will be given 30 minutes before treatment administration.
- h. Samples collected for plasma pharmacokinetic analysis will be processed per the instructions in Appendix 1.

\*Three timepoints before dosing: -45, -30, and -15 minutes.

NOTE: When ECG extractions coincide with safety ECGs, vital signs assessments, and/or blood draws, then procedures should be carried out in said order.

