**Starting dose for the SAD**

A single dose of 50 mg appears to be an appropriate starting dose for the single ascending dose SAD study for the following reasons:

- The proposed 33-fold safety margin to the human equivalent dose (HED) derived from the no-observed-adverse-effect level (NOAEL, 100 mg/kg) in the 28-day dog toxicology study is based on twice daily dosing (50 mg/kg BID) compared to once daily dosing proposed in humans. The daily dosing frequency was changed from QD to BID in the animal studies to increase tolerability of TBI-223 when orally administered to dogs.
- The more relevant NOAEL at 50 mg/kg QD (HED 27 mg/kg) in the repeat-dose 28-day dog toxicology study provides a 17-fold safety margin to a first-in-human (FIH) starting dose of 100 mg QD. However, in the nonclinical safety pharmacology cardiovascular study in dogs, a trend of increasing QTc prolongation was observed in dogs after a single oral administration of TBI-223 at 50 and 100 mg/kg (max increase 11 to 14 msec from baseline, 12 msec from control 2 hours post-dose) at 1 to 13 hours post-dose, and a statistically significant increase in QTc interval was detected at 200 mg/kg (mean increase 22 msec from baseline and control 2 to 5 hours post-dose, and 21 to 25 hours post-dose).
- Significant toxicity was observed in the 28-day dog toxicology study at a dose of 200 mg/kg/day (100 mg/kg BID) including intermittent and continuous tremors, ataxia, convulsions in several animals, QTc prolongation (10 to 11% baseline), decreased body weight, and vomitus. It should be noted that the dosing interval between twice daily dosing was not provided, and the clinical observations were

- performed at 1 and 12 hours post-dose, and not 2 to 4 hours at  $C_{max}/T_{max}$  when tremors may have a greatest chance of occurring and being detected.

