#### 6.9.7 Cardiac Holter Monitoring, and Cardiodynamic Assessment

In order to detect potential changes in ECG parameters, study subjects will undergo cardiac Holter monitoring. Holter monitoring will begin approximately 24 hours before dosing and continue for at least 48 hours after dosing.

On Day -2 and Day -1, subjects should fast until lunch to avoid circadian fluctuations.

In addition, replicate ECGs will be obtained after dosing, specifically around the estimated Tmax (which is estimated to be around 3 hours after dosing; although the timing may be altered based on generated phase 1 pharmacokinetic data). ECG data will be analyzed focusing in particular on changes of the QT segment although other ECG parameters will be analyzed, as specified in the Statistical Analysis Plan (SAP).

Continuous 12-lead ECGs (Holter) will be recorded for 24 hours prior to dose and for at least 48 hours post dose. The ECG waveforms will be stored for analysis as appropriate after the completion of the study. Replicate 12-lead ECGs will be extracted prior to dosing and serially after dosing by the central ECG laboratory at the time points shown in Table 9. At each time point for ECG extraction, subjects should be resting in the supine position for at least 10 minutes.

NOTE: When ECG extractions coincide with safety ECGs, vital signs assessment and blood draws, procedures should be carried out in said order.

Details regarding the equipment and methods to be used for continuous Holter extraction and analysis are provided in Appendix 4.

Part 2 of the study will not have cardiac Holter monitoring.

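### Part 2's ECG footnotes, carried over from Part 1, rely on a Holter that is not worn and put the only post-dose replicates at 48 hours, leaving single tracings near peak exposure

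*Protocol*

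**What the plan says.** **Replication in Part 2.** Protocol Table 16 footnote d: "TriPLICATE ECGs will be completed at screening, Day -2, Day -1, and at 48 hours only". It continues: "All other time points will be single ECG readings within 15 minutes at time points within flowchart".

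**Holter in Part 2.** Appendix 6: "Cardiac telemetry and Holter recording will not be performed during Part 2". Section 6.9.7 ends the same way: "Part 2 of the study will not have cardiac Holter monitoring". Yet Table 16 footnote e says "All safety ECGs on Day 1 and Day 2 will be extracted from a continuous 12 lead Holter recording".

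**Timing around the peak.** Section 1.4 (Cardiovascular Monitoring) wants ECG timing guided by PK data so that collection falls around the estimated Tmax. Section 6.9.7 says "replicate ECGs will be obtained after dosing, specifically around the estimated" Tmax, which it puts at about 3 h. Appendix 6 keeps all protocol procedures for Part 2 except those it lists.

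**Analysis.** SAP 6.12.4 tabulates observed QTcF and change from baseline by treatment group and time. SAP 6.2.7 averages multiple values at a time point. SAP 6.2.2 takes the last non-missing pre-dose value as baseline.

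**The concern.** QTc prolongation is one of the two nonclinical signals on which Section 1.4 builds the monitoring. Part 2 gives 1800 mg SR tablets fed and 2000 mg IR tablets fasted and fed, without placebo. What it learns about QT therefore comes from within-arm changes in six subjects.

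In Part 1 the same footnote wording did no harm. Table 9 footnote m and Appendix 4 supply ten Holter-extracted replicates at each extraction time, so the safety ECGs did not have to carry the precision. Part 2 drops the Holter and keeps the footnote. Its only post-dose replication then falls at 48 h, far from the estimated peak, and readings where a drug effect is most likely are single.

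**Working it through.** **1. Is the wording carried over?** Table 16 footnotes d and e match Table 9 footnotes e and f.

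| Item | Table 16 footnotes | Rest of the Part 2 plan |
|---|---|---|
| Day -2 triplicate | named in footnote d | check-in is on Day -1 (Section 6.3, Appendix 6); no Day -2 visit |
| Source of Day 1-2 safety ECGs | Holter extraction, footnote e | no Holter (Section 6.9.7, Appendix 6) |
| Post-dose replicates | 48 h only, footnote d | Section 1.4 wants ECGs around Tmax; Section 6.9.7 can be read as wanting replicates there |

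Footnote e would not restore replication even if a Holter existed, because footnote d still makes those readings single.

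**2. What it costs in precision.** The documents state no QT precision figure, so there is none to reproduce.

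Inputs:
- n = 6 per arm (protocol synopsis, Cohort 8).
- k = 1 or 3 tracings averaged (footnote d; SAP 6.2.7).
- t(0.95, 5 df) = 2.015.
- Single-tracing SD s = 6-10 ms. This is an assumption.
- Tracings independent, the best case for replication. Only measurement noise is counted.

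Formulas: SD of change = s × sqrt(1/k_post + 1/k_base). Half-width of the 90% CI = 2.015 × SD of change / sqrt(6).

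| Post-dose / baseline | SD of change | s = 6 | s = 8 | s = 10 |
|---|---|---|---|---|
| single / single (peak, as written) | sqrt(2) × s | 7.0 | 9.3 | 11.6 |
| triplicate / single | sqrt(4/3) × s | 5.7 | 7.6 | 9.5 |
| triplicate / triplicate | sqrt(2/3) × s | 4.0 | 5.4 | 6.7 |

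For example, with s = 6: 2.015 × 8.49 / 2.449 = 7.0 ms.

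The second row also describes 48 h as the plan stands, so the arm mean is estimated better at 48 h than near the peak.

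**3. Which baseline applies?** Footnotes d and e provide for a pre-dose ECG, and footnote d makes it a single reading. Under SAP 6.2.2 that tracing becomes the baseline. Moving the triplicate alone therefore gains a factor of sqrt(2)/sqrt(4/3) = 1.22. The full factor of 1.73 needs a triplicate baseline as well. The asterisk under Table 16 lists three pre-dose times, but in Table 9 it belongs to the Holter-extraction row, so it does not secure a replicate baseline here.

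**4. Sensitivity.** Add a time-to-time SD that replication cannot reduce (also assumed), with s = 6-10 ms:

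| Time-to-time SD | single / single | triplicate / single | triplicate / triplicate |
|---|---|---|---|
| 5 ms | 9.1-13.0 | 8.1-11.1 | 7.1-8.9 |
| 8 ms | 11.6-14.9 | 10.9-13.3 | 10.1-11.5 |

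The gain persists but is smaller.

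**The case against.** **Section 6.9.7 may not conflict with footnote d.** The sentence on replicates sits in the Holter section, which refers to extraction by the central laboratory at the Table 9 times and ends by excluding Part 2 from Holter. It may mean Holter extractions only. A reader might infer a flat contradiction; the text allows that reading but does not compel it. The clear contradictions are footnote e and Day -2. On the narrower reading, Part 2 simply has no replicates near the peak, and moving the triplicate is a design improvement, not a correction.

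**Part 1 already covers QT.** Part 1 has placebo, Holter and ten replicates per extraction time, at doses up to 2600 mg. This stands, and it limits the importance of the point. It is not complete cover: the only fed group in Part 1 is the 1200 mg suspension (SAP 6.3).

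**Part 2 ECGs are for on-site safety review, with repeat testing, and the study is not powered.** This also stands. But repeat testing under footnote d is tied to QTcF above 500 ms or a change above 60 ms, and does not improve the arm means in SAP 6.12.4.

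**The peak may not be at 3 h.** The documents give no Tmax for the SR tablets or the fed state, and SR fed arms are 18 of the 24 Cohort 8 subjects. A triplicate fixed at 3 h could miss their peak. The ECG row of Table 16 is also absent from the extracted text, so an ECG at 3 h cannot be confirmed; that gap is not an error in the plan. Under footnote d, any post-dose time other than 48 h is single.

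**Conclusion.** The point holds as a reconciliation item with a modest, cheap gain in precision. Footnotes d and e need correcting whatever view is taken of replication. As written, they rely on a recording that Part 2 does not make and place its only post-dose replicates at 48 h.

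Under the stated assumptions, the 90% half-width near the peak goes from 7.0-11.6 ms to 5.7-9.5 ms by moving the triplicate, and to 4.0-6.7 ms only with a triplicate baseline too. Only the 1.73 factor on tracing-to-tracing SD is free of the assumed SDs.

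Three stronger inferences are not supported:
- That the peak reading is the least precise in Part 2. It ties with every other single tracing.
- That moving the triplicate alone reaches 4.0-6.7 ms. SAP 6.2.2 does not secure the baseline this needs.
- That the dog result ("max increase 11 to 14 msec from baseline, 12 msec from control 2 hours post-dose") sets a human target. It is described as a trend, and neither document uses it as a benchmark.

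**What to change.** 1. **Table 16 footnote d:** delete Day -2. Place the Part 2 post-dose triplicate at the scheduled ECG time nearest the estimated Tmax instead of 48 h. That is about 3 h in the protocol, to be updated from PK data for the fed and SR arms.
2. **Table 16 footnote e:** delete the Holter-extraction sentence. Check the asterisk and the closing note on ECG extractions for the same carry-over.
3. **Section 6.9.7 and Appendix 6:** state whether the sentence on Tmax replicates covers Part 2.
4. **SAP 6.2.2:** define the Part 2 QTcF baseline as the mean of the Day -1 triplicate.
5. **Section 6.9.6:** reconcile it with Section 1.4 and SAP 6.12.4. It says safety-ECG intervals are not noted unless part of an AE, while the other two record and tabulate them.

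**Cost.** No extra visit, and no change to any dose, threshold or stopping rule. The 48 h ECG becomes a single reading. The tracing count stays the same (3 + 1 instead of 1 + 3) only if one time point is replicated. A Day -1 baseline lies further from dosing than a pre-dose tracing, so day-to-day and time-of-day differences enter the change.

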2.0	28-Apr-20	
SAP v2.0 has been updated in line with Protocol v3.0, dated 21-Jan-2020. The following changes affecting the analyses described in SAP v1.0, dated 05-March-2019 are as follows:
 
Changes to dose cohorts
 
TBI-223 (1400 mg) suspension was replaced with TBI-223 (2000 mg) suspension.
 
TBI-223 (2600 mg) suspension cohort was added
 
TBI-223 300 mg oral capsule repeat cohort was added.
 
Study Part 2 was added, including,
 
 - Arm 1 - TBI-223 SR Tablets 600 mg (Prototype 1). Dose of 1800 mg (3 tablets of 600 mg), under fed conditions - Arm 2 - TBI-223 SR Tablets 600 mg (Prototype 2). Dose of 1800 mg (3 tablets of 600 mg), under fed conditions - Arm 3 - TBI-223 SR Tablets 900 mg (Prototype 3). Dose of 1800 mg (2 tablets of 900 mg), under fed conditions - Arm 4 - TBI-223 IR Tablets 1000 mg. Dose of 2000 mg (2 tablets of 1000 mg), under fasting conditions - TBI-223 IR Tablets 1000 mg. Dose of 2000 mg (2 tablets of 1000 mg), under fed conditions. 
Changes to safety analyses
 
All Enrolled Subjects analysis set was added.
 
Subject Disposition will be summarized for All Enrolled Subjects rather than the Randomized Set.

QMD Ref: Worldwide-TMP-ST-006-4.0 Effective: 12Aug2019	Governing QMD: Worldwide-SOP-ST-001
Confidentiality Statement	

This document is the property of Worldwide Clinical Trials Inc. and may not be duplicated, copied, altered or removed from company without prior approval from Worldwide Quality Assurance or in compliance with Worldwide Standard Operating Procedures.

Worldwide Clinical Trials Controlled Quality Management Document			
 WORLDWIDE CLINICAL TRIALS	Sponsor:	TB Alliance	
	Protocol Number:	TBI-223-CL-001	
STATISTICAL ANALYSIS PLAN – PHASE 1			

Version	Issue Date	Revision/Addition
		
Safety data will be tabulated by study part, period (where applicable) and treatment group.
 
SAP sections 4 Sample Size and 5 Randomization were updated to reflect study Parts 1 and 2.
 
Changes to PK analyses
 
As of SAP v2.0, PK concentration and parameter data will also be stratified by gender.
 
Description of PK analyses and outputs were updated to reflect protocol and dose group changes.

QMD Ref: Worldwide-TMP-ST-006-4.0 Effective: 12Aug2019	Governing QMD: Worldwide-SOP-ST-001
Confidentiality Statement	

